Appendix 6: Waist Circumference Measurement

Waist is taken at the midpoint between the lower rib margin and the iliac crest in cms; 3 separate measurements will be performed and recorded in the CRF at each visit where waist circumference is recorded.

Waist circumference >88 cm in women or >102 cm in men define abdominal obesity (ref NCEP ATP III definition of the metabolic syndrome)

- The circumference should preferably be measured on subjects while they are semi-clothed, i.e. waist uncovered with the subjects wearing underclothes only. If it is not possible to follow this procedure, the alternative is to measure the circumference on subjects without heavy outer garments with all tight clothing, including the belt, loosened and with the pockets emptied.
- Patients should stand with their feet fairly close together (about 12-15 cm) with their weight equally distributed on each leg. Participants should be asked to breathe normally and at the time of the reading of the measurement asked to breath out gently. This will prevent subjects from contracting their muscles or from holding their breath.
- A plastic metric tape should be used. The tape should be held firmly and its horizontal position should be ensured. It is recommended that the observer sit beside the participant while the readings are taken. The tape should be loose enough to allow the recorder to place one finger between the tape and the subject's body. The importance of the tightness of the tape should be emphasized in training.

Appendix 7: Ankle-Brachial Index measurement

- a) Measure highest systolic reading in both arms
 - 1. Record first Doppler sound as cuff is deflated
 - 2. Record at the radial pulse
 - 3. Use highest of the two arm pressures

- b) Measure systolic readings in both legs
 - 1. Cuff applied to calf
 - 2. Record first Doppler sound as cuff is deflated
 - 3. Use Doppler ultrasound device

- c) Record dorsalis pedis (DP) pressure

- d) Record posterior tibial (PT) pressure
 - 1. Use highest ankle pressure (DP) or (PT) for each leg

- e) Calculate ratio of each ankle to brachial pressure
 - 1. Divide each ankle by highest brachial pressure

Appendix 8: Intima-Media Thickness measurement

Carotid intima-media thickness (IMT) is a marker of early arterial change of the arterial walls including atherosclerosis and/or vascular hypertrophy, detected by B-Mode ultrasonography.

1. Recommendations for ultrasonographic examinations:

- Machines equipped with 5 or 7 MHz transducers
- Subjects in the supine position
- ECG signal used for synchronizing the image analysis to the end of the diastole
- Doppler ultrasound used for vessel identification (and information on blood flow velocity)
- Carotid artery scanned at the level of the bifurcation, with the head turned to the opposite side (e.g. to the right for left carotid artery)
- Examined region:
 - 30 mm of the common carotid artery
 - carotid bulb
 - 10 mm each of the internal and external carotid arteries
- Regions scanned with both longitudinal and transverse projections, in order to assess the occurrence of plaques
- Three "frozen" images recorded for assessment of intima-media thickness and lumen diameter
- Optimal image projection considered to be achieved when ultrasound beams are perpendicular to the far vessel wall

2. Recommendations for assessments of intima-media thickness¹ and lumen diameter²

- Ultrasonographic images analyzed with a computerized system
- Intima-media thickness measured in a 10 mm long segment just proximal to the carotid bulb in the common carotid artery
- Calculation by the computer program of the minimum, maximum and mean values of intima-media thickness from three separate images

3. Assessments of plaques

- A plaque is defined as a distinct area with an intima-media thickness exceeding twice that of the neighboring sites

¹ Intima-media thickness is defined as the distance from the leading edge of the lumen-intima interface to the leading edge of the media-adventitia interface of the far wall

² Lumen diameter is defined as the distance between the leading edges of the intima-lumen interface of the near wall and the lumen-intima interface of the far wall

- Classification of plaques, according to a four-graded semi-quantitative scale of their size/severity:
 - Grade 0: no plaque
 - Grade 1: small localized plaque/wall thickening
 - Grade 2: moderate plaque with <50% lumen diameter stenosis
 - Grade 3: circumferential and/or large plaque with ≥50% lumen diameter stenosis
- Plaques detection must be focused on the distal part of the common carotid artery, the carotid bulb or in the proximal parts of the internal or external carotid artery.

1. INTRODUCTION

Rimonabant is being studied in CRESCENDO to see whether its use is associated with a reduction in myocardial infarction, stroke, or cardiovascular death in abdominally obese patients at increased risk for cardiovascular events. In earlier trials, rimonabant use has been shown to be associated with an increase in HDL-cholesterol, a decrease in triglycerides, and an improvement in insulin sensitivity and glycemic control. This substudy is being conducted to demonstrate that rimonabant has beneficial effects on these metabolic risk factors for cardiovascular events, in conjunction with a demonstrable beneficial effect on cardiovascular event.

2. PRIMARY OBJECTIVE

To evaluate the effect of rimonabant 20 mg OD on fasting HDL-cholesterol, fasting LDL-cholesterol, fasting triglyceride, fasting plasma glucose, fasting insulin, and fasting HbA1c levels.

3. STUDY DESIGN

Patients randomized in the multinational, multicenter, double-blind, placebo-controlled parallel group CRESCENDO study at selected sites will be asked to participate in this substudy. Once written informed consent is obtained, patients will have blood drawn, after an overnight fast, at baseline, at every 6-month visit, and at the end of study visit. Blood samples will be analyzed at a Central Laboratory, and the Investigators, patients, and Sponsor personnel will be blinded to the results.

4. SELECTION OF PATIENTS

Sites selected to participate in this substudy will have IRB/EC approval for the main CRESCENDO study and for this substudy and separate informed consent. All subjects must meet eligibility criteria for the main CRESCENDO study, must give written informed consent for that study, and must also give written informed consent for this substudy. Approximately 3000 patients will be expected to participate in this substudy. There are no separate inclusion or exclusion criteria for this substudy, besides the requirement for written informed consent. Patients who have consented to participate in the main study but refuse participation in this substudy will be allowed to continue in the main study.

5. STUDY PROCEDURES

After an overnight fast, patients will have blood samples drawn for HDL-cholesterol, LDL-cholesterol, triglyceride, plasma glucose, insulin, and HbA1c measurements at baseline, at every 6-month visit, and at the end of study visit. An additional blood sample will be drawn for other metabolic testing that may become indicated. Blood samples will be processed at the site in accordance with directions provided by the Central Laboratory, and shipped to the Central Laboratory facility for analysis. The results of these analyses will be maintained by the Central Laboratory, and the results, coded by patient's initials,

gender, and date of birth, patient's study number, and date blood sample was obtained, will be sent to the Sponsor for loading into the study database. The Investigators and the patients will be blinded to the results.

6. WITHDRAWAL OF CONSENT

Patients may withdraw consent from participation in this substudy at any time. If they do so, they may continue full participation in the main CRESCENDO study. If they withdraw from study medication, they may continue in this substudy.

7. PRIMARY STATISTICAL ANALYSIS

Changes in fasting HDL-cholesterol, fasting LDL-cholesterol, fasting triglyceride, fasting plasma glucose, fasting insulin, and fasting HbA1c levels at each point in time from baseline will be analyzed and the results compared between the rimonabant and placebo groups, using an analysis of covariance (ANCOVA), with the baseline value as covariate, with a significance level of 0.05.

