Rimonabant has recently been studied in several large clinical trials. The trials and their specific efficacy and safety results are summarized in the Clinical Investigator's Brochure. Four double-blind, placebo-controlled Phase 3 studies were conducted to examine the effects of rimonabant on waist circumference, high serum triglycerides, low HDL-cholesterol and glucose control in patients with metabolic syndrome, and on weight management, type 2 diabetes, and obesity-related dyslipidemia. Each study, RIO-North America, RIO-Europe, RIO-Lipids, and RIO-Diabetes, had as its primary endpoint weight loss and weight maintenance at one year. Each study was conducted in overweight or obese patients with other cardiovascular risk factors. RIO-North America and RIO-Europe assessed prevention of weight regain, weight maintenance, and related metabolic risk factors over two years. RIO-Lipids, conducted in dyslipidemic obese patients, evaluated the effects of rimonabant on lipids and glucose tolerance. RIO-Diabetes, conducted in overweight and obese type 2 diabetics, evaluated the effects of rimonabant on hemoglobin A1c (HbA1c), fasting plasma glucose, and lipids. In each study a hypocaloric diet was prescribed and exercise was recommended. Over 6600 patients received rimonabant at either a 5 or 20 mg daily dose.

Statistically significant and clinically meaningful mean weight reductions from baseline to one year for rimonabant 20 mg versus placebo were demonstrated in these four large trials. Additionally, rimonabant 20 mg was effective in maintaining weight loss to two years in the RIO-North America and RIO-Europe trials.

In RIO-Diabetes, the group receiving rimonabant 20 mg for one year demonstrated statistically significant improvements in HbA1c and fasting plasma glucose compared with the placebo group. In addition to the improvement in glycemic parameters, there were significant improvements in lipid parameters and the metabolic syndrome in this diabetic population receiving rimonabant.

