In addition to the beneficial effects of rimonabant 20 mg on the lipid profile observed in the RIO-Lipids trial, effects on LDL particle size and adiponectin levels were measured in a subset of patients in this trial. Compared to placebo, the LDL particle size distribution shifted to larger, less dense and less atherogenic particles in patients treated with rimonabant 20 mg. There was also a significantly greater increase in plasma adiponectin levels at one year in those receiving rimonabant 20 mg compared to those on placebo.

In patients with the metabolic syndrome at baseline from all four studies, improvements in the risk parameters specified in the NCEP ATP III guidelines for the diagnosis of metabolic syndrome were seen. At one year, rimonabant 20 mg was effective in reducing waist circumference and triglycerides and increasing HDL-cholesterol. Fasting plasma glucose was significantly reduced in diabetics. Rimonabant 20 mg was effective in reducing the number of patients with metabolic syndrome regardless of which risk parameters led to this diagnosis. In both two-year clinical trials (RIO-North America and RIO-Europe), improvements in the risk parameters of the metabolic syndrome were maintained over the two years of treatment with rimonabant.

In all clinical trials of rimonabant, the safety profile and tolerability has been acceptable. No significant safety concerns have been raised in these trials.

In summary, use of rimonabant, at a 20 mg daily dose, has been associated with significant weight loss and a decrease in waist circumference compared to placebo in several clinical trials. Other effects seen in some of the trials include a significant increase in HDL-cholesterol and adiponectin, and decreases in triglycerides, in small, dense atherogenic LDL particles, and in C-reactive protein. Insulin sensitivity was improved with rimonabant treatment, in patients in whom this was studied. The proportion of obese patients with the metabolic syndrome, as diagnosed at study entry, was cut in half after one year of treatment with rimonabant. These effects were maintained over two years with continued drug treatment. Importantly, the metabolic effects of rimonabant could not be explained on the basis of weight loss alone. Thus, rimonabant demonstrated favorable effects on metabolic cardiovascular risk factors independent of weight loss.

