- current intermittent claudication (WHO criteria, eg, leg pain occurring only while walking and disappearing in less than 10 minutes on standing) of presumed atherosclerotic origin **TOGETHER WITH** ankle-brachial index equal to or less than 0.85 in either leg at rest, OR
 - history of intermittent claudication (WHO criteria as above) **TOGETHER WITH** either previous intervention by amputation, or reconstructive vascular surgery, or angioplasty in one or both legs because of atherosclerotic disease,
- e) Type 2 diabetes mellitus (fasting plasma glucose equal to or greater than 126 mg/dL [7.0 mmol/L] on two or more occasions)

Major cardiovascular risk factors:

- f) Metabolic syndrome, **as diagnosed by the presence of at least 2 of the following risk factors (if 3 of the risk factors listed below are fulfilled, this is equivalent to two major risk factors and the patient is eligible):**
- Fasting triglyceride level equal to or greater than 150 mg/dL (1.69 mmol/L)
 - HDL-cholesterol less than 40 mg/dL (1.03 mmol/L) for males or less than 50 mg/dL (1.28 mmol/L) for females
 - Fasting plasma glucose equal to or greater than 110 mg/dL (6.1 mmol/L)
 - Blood pressure equal to or greater than 130 mm Hg systolic and/or 85 mm Hg diastolic at baseline visit
- g) Cerebrovascular disease (**at least one of the following three criteria** must be satisfied):
- Asymptomatic disease of the carotid, intracranial, and/or vertebral arteries, with greater than 50% stenosis
 - At least one carotid plaque on ultrasonography, defined as a distinct area with an intima-media thickness (IMT) exceeding twice that of neighboring sites, OR
 - Prior cerebrovascular revascularization procedure
- h) Renal artery disease, with greater than 60% stenosis on MR angiography, CT angiography, or angiography, or prior revascularization procedure
- i) Previous history of abdominal aortic aneurysm repair
- j) Asymptomatic ankle-brachial index less than 0.85
- k) Elevated hs-CRP greater than 3 mg/L
- l) Males 65 years or older or females 70 years or older

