13.4.1.3 General statistical approach

All statistical tests will be two-sided.

All summary tables for quantitative parameters will display mean, standard deviation, median, range (minimum and maximum), as well as number of missing data (if relevant). All summary tables for qualitative parameters will display counts, percentages and number of missing data if relevant.

Baseline data are defined as the last measurement performed before the first study drug intake.

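### The Metabolic Substudy should report HbA1c and fasting glucose effects by diabetes status beside the pooled ANCOVA, and use diabetes status as a covariate for these two markers

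*Protocol*

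**What the plan says.** Appendix 9, section 7 compares rimonabant with placebo on "Changes in fasting HDL-cholesterol, fasting LDL-cholesterol, fasting triglyceride, fasting plasma glucose, fasting insulin, and fasting HbA1c levels at each point in time from baseline", "using an analysis of covariance (ANCOVA), with the baseline value as covariate, with a significance level of 0.05". It names no diabetes term and no estimate by diabetes status.

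Appendix 9, section 4 sets the sample: "Approximately 3000 patients will be expected to participate in this substudy", and "There are no separate inclusion or exclusion criteria for this substudy, besides the requirement for written informed consent". In the main trial, diabetes is one of several ways to qualify (Section 7.2, criterion 4e: "Type 2 diabetes mellitus (fasting plasma glucose equal to or greater than 126 mg/dL" and so on). Randomization is stratified by center only (Section 8.3).

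Section 4.2 gives the prior evidence:

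- The one-year trial in diabetics showed "statistically significant improvements in HbA1c and fasting plasma glucose compared with the placebo group".
- For metabolic-syndrome patients from all four trials, waist, triglycerides and HDL-cholesterol are reported without restriction, but for glucose the text is "Fasting plasma glucose was significantly reduced in diabetics".
- In the three trials of non-diabetics, pre-diabetic patients are said to have better glucose control, seen as a lower insulin requirement.

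**The concern.** The plan gives one number per glycemic marker for two groups that its own background treats differently. HbA1c and fasting glucose have little room to fall in patients who start near normal, and the reported gains on these two markers come from diabetics. If the effect differs by diabetes status, the pooled difference depends on how many diabetics the selected sites enroll. A reader could then underestimate the effect in diabetics and overestimate it in everyone else.

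There is also a smaller question of precision. If the two groups change differently from the same baseline value, leaving diabetes out of the model adds avoidable residual variance. If estimates by diabetes status are requested only after unblinding, they become post hoc subgroups.

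**Working it through.** The substudy states no power, SD, effect size or diabetic share, so there is no planned figure to reproduce. From the documents: about 3,000 patients, taken as 1,500 per arm because the main trial allocates equally (Section 7.1); ANCOVA on baseline; level 0.05, two-sided if the main rule applies ("All statistical tests will be two-sided"). Everything else below is assumed for illustration.

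**1. Dependence on case mix.** Pooled effect = p·τD + (1 − p)·τN, where p is the diabetic share and τD, τN are the effects in diabetics and others. With τD = -0.60 and τN = -0.05 HbA1c points:

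- p = 0.3: -0.180 - 0.035 = -0.215
- p = 0.5: -0.300 - 0.025 = -0.325
- p = 0.7: -0.420 - 0.015 = -0.435

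**2. Pooled against separate estimates.** Take p = 0.4, τD = -0.5, τN = 0, and residual SD 1.0 in diabetics and 0.35 in others.

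- Average residual variance W = 0.4 × 1.0² + 0.6 × 0.35² = 0.4735
- Pooled: effect -0.20, SE = √(2 × 0.4735 / 1500) = 0.0251, z = 7.96
- Diabetics only (600 per arm): effect -0.50, SE = √(2 × 1.0 / 600) = 0.0577, z = 8.66
- Others (900 per arm): SE = √(2 × 0.1225 / 900) = 0.0165
- Difference between strata: SE = √(0.0577² + 0.0165²) = 0.060

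Both stratum effects and their difference are estimable at this size, but the diabetic-only SE is more than twice the pooled one.

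**3. Power.** With 1,500 per arm and effects in diabetics of 0.3 to 0.7, pooled power is 0.98 or more at 40% to 60% diabetic. At 20% diabetic and an effect of 0.3 it is 0.72 to 0.85, against 0.87 to 0.96 in diabetics only. With 1,000 analyzed per arm, those ranges are 0.55 to 0.69 and 0.71 to 0.85. Power suffers materially only with few diabetics and a small effect.

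**4. What the covariate buys.** Let g be the difference in mean change between strata at the same baseline value, averaged over arms. Let R² be the squared correlation of diabetes status with baseline HbA1c, and h = ((τD − τN)/2)²·p(1 − p). The residual variance is W + h + g²·p(1 − p)(1 − R²) with baseline only, and W + h once diabetes status is added. Assume baseline HbA1c 7.5 (SD 1.1) in diabetics and 5.7 (SD 0.35) in others, with p = 0.4 and the effects and SDs of step 2:

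- R² = 0.7776 / (0.7776 + 0.5575) = 0.582, where 0.7776 = 0.24 × 1.8² and 0.5575 = 0.4 × 1.1² + 0.6 × 0.35²
- h = 0.25² × 0.24 = 0.015

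| g | Omitted variance | Reduction |
|---|---|---|
| 0 | 0 | 0% |
| 0.2 | 0.0040 | 0.8% |
| 0.3 | 0.0090 | 1.8% |
| 0.6 | 0.0361 | 6.9% |
| 0.8 | 0.0641 | 11.6% |

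Shares of 20% and 60% give nearly the same reductions. Simulation under these inputs agreed and left the pooled estimate at -0.20 with or without the covariate. Other assumed HbA1c distributions, with drifts of 0 to 0.6 points, gave SE ratios from 0.989 down to 0.889, that is, variance cuts of 1 − 0.989² = 2% to 1 − 0.889² = 21%. The gain depends on g, on which the documents are silent.

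**The case against.** The strongest reply is that nothing here is wrong. Appendix 9, section 2 asks for the effect of rimonabant on the six markers, and Section 14 places this in a subset of trial patients. Under randomization, baseline-adjusted ANCOVA estimates that average effect without bias. Calling it diluted makes sense only against another target, the effect in diabetics, which the objective does not name. This stands.

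Second, a reader might infer from Section 4.2 that the glycemic effect is confined to diabetics. The text does not support that. It reports better glucose control in pre-diabetics through insulin requirement, and fasting insulin is itself a substudy marker. It names HbA1c as an outcome only for the diabetes trial, so its silence on HbA1c elsewhere is not evidence of no effect. What remains is that the reported HbA1c and fasting-glucose gains come from diabetics.

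Third, a diabetes covariate does not change what the pooled estimate measures. Only separate estimates or an interaction show how the effect varies. This also stands.

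Fourth, such detail may sit in an analysis plan that is not shown. That is possible, and it is why this cannot be called an omission. But Section 13.1 makes Section 13 the basis of the main analysis plan, while Section 14 gives the substudies their own protocols and fully separate analysis. Appendix 9 already fixes the primary model, so the sentence belongs there.

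Finally, the main-study baseline laboratory panel contains no glucose, and a patient who qualifies by another route need not document criterion 4e. But Section 12.1.2 records compliance with the inclusion criteria and relevant medical history, and the substudy draws baseline glucose and HbA1c. Diabetes status can therefore be derived, provided the rule is written down.

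**Conclusion.** The point holds as an inexpensive improvement, not as an error. The pooled ANCOVA is valid for the stated objective. If the effect differs by diabetes status, the HbA1c and glucose differences will depend on the diabetic share at the selected sites and describe neither group. On the assumed effects, that means about -0.22 to -0.44 HbA1c points as the share goes from 30% to 70%.

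The precision gain is secondary: roughly 1% to 13% of the variance on most assumed inputs, nil if the strata do not differ at a given baseline value, and about 21% in the most extreme case tried. Every size here rests on assumed shares, SDs, effects and drifts.

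The documents do not support three stronger readings: that the pooled result is biased, that it should be demoted to descriptive, or that lipids and insulin need the same term. No main-trial conclusion is affected, since the substudy is analyzed and reported separately.

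**What to change.** In Appendix 9, section 7, for HbA1c and fasting plasma glucose only:

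- Add type 2 diabetes at randomization (yes/no) as a covariate, and state how it is derived from the recorded inclusion criteria and medical history.
- Keep the pooled ANCOVA as the primary analysis.
- Prespecify a treatment-by-diabetes term, and report the treatment difference with its 95% CI separately for diabetic and non-diabetic patients beside the pooled result.

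The cost is one or two sentences, made before unblinding. No visits, samples or patients are added. The report should note that the diabetic-only estimate will have a larger SE than the pooled one.
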